6. BASELINE, EFFICACY AND SAFETY EVALUATIONS

6.1 Schedule of Evaluations

The assessments to be conducted at each scheduled visit are displayed in the following table.

Distribution:

Original:

Copy:

TPCA025 Version 2 (based on TPQA036 Version 2) CONFIDENTIAL AND PROPRIETARY

Page 18 of 80

Sponsor:	AstraZeneca AB	Protocol/CIP Number:	D7550C00003
CIL Project Number:	40343		

Table 2: Study assessment schedule

	ACS event	Visit 1 Screening	Visit 2 Randomization	Visit 3 (2 weeks) During Treatment	Visit 4 (4 weeks) During Treatment	Visit 4b (8 weeks) During Treatment	Visit 4c (12 weeks) End of Treatment	Visit 5 Follow-up	Comments
Study Day	-7 days	X ^a	day 1	day 14	day 28	28 days after Visit 4	28 days after Visit 4b	28 days after last dose	
Time Window		1-5 days post ACS event	7-28days post ACS event	±2	±3	±2	±3	±4 days	6
Informed consent (ICF)		X							
Inclusion/exclus ion criteria		x	X						
Demographic data		X							Smoking history and alcohol consumption to be included
Height		x							
Body weight ^b		x	x	X	x	2	x	x	
Collect date for ACS event		x				£			
TIMI flow score		x					y		
Medical and surgical history		x							6

Distribution:

Original:

Page 19 of 80

Copy:

TPCA025 Version 2 (based on TPQA036 Version 2) CONFIDENTIAL AND PROPRIETARY Effective Date: 27th August 2017 Prior Effective Date: 21st December 2016

Sponsor:	AstraZeneca AB	Protocol/CIP Number:	D7550C00003
CIL Project Number:	40343		

	ACS event	Visit 1 Screening	Visit 2 Randomization	Visit 3 (2 weeks) During Treatment	Visit 4 (4 weeks) During Treatment	Visit 4b (8 weeks) During Treatment	Visit 4c (12 weeks) End of Treatment	Visit 5 Follow-up	Comments
Study Day	-7 days	X ^a	day 1	day 14	day 28	28 days after Visit 4	28 days after Visit 4b	28 days after last dose	
Time Window		1-5 days post ACS event	7-28days post ACS event	±2	±3	±2	±3	±4 days	
Concomitant medication		x	X	X	x	x	x	x	
Serology	÷	x							
FSH and luteinizing hormone (LH) sampling (females only)		x							
Randomization			x						
Diary card hand-out			X						
Diary card review				x	х	x	X		
Diary card hand-in							x		
IP dispensed			x		x	x			8
IP returned	4				x	x	x		

Distribution:

Original:

Page 20 of 80

Copy:

TPCA025 Version 2 (based on TPQA036 Version 2) CONFIDENTIAL AND PROPRIETARY

Sponsor:	AstraZeneca AB	Protocol/CIP Number:	D7550C00003
CIL Project Number:	40343		

	ACS event	Visit 1 Screening	Visit 2 Randomization	Visit 3 (2 weeks) During Treatment	Visit 4 (4 weeks) During Treatment	Visit 4b (8 weeks) During Treatment	Visit 4c (12 weeks) End of Treatment	Visit 5 Follow-up	Comments
Study Day	-7 days	X ^a	day 1	day 14	day 28	28 days after Visit 4	28 days after Visit 4b	28 days after last dose	
Time Window		1-5 days post ACS event	7-28days post ACS event	±2	±3	±2	±3	±4 days	
IP intake at the clinic			X	X	x		x		
Safety and tolerability:						£.			c.
Adverse event (AE) review		x (SAE only)	X	x	x	x ^m	x	x	
Blood pressure and pulse rate (supine)		x	x	x	x		x	x	
12-lead pECG with electronic source file		X	x	х	x		x	x	
Physical examination ^c		x	x	X	x		X	x	

Distribution:

Original:

Page 21 of 80

Copy:

TPCA025 Version 2 (based on TPQA036 Version 2) CONFIDENTIAL AND PROPRIETARY

Sponsor:	AstraZeneca AB	Protocol/CIP Number:	D7550C00003
CIL Project Number:	40343		

	ACS event	Visit 1 Screening	Visit 2 Randomization	Visit 3 (2 weeks) During Treatment	Visit 4 (4 weeks) During Treatment	Visit 4b (8 weeks) During Treatment	Visit 4c (12 weeks) End of Treatment	Visit 5 Follow-up	Comments
Study Day	-7 days	X ^a	day 1	day 14	day 28	28 days after Visit 4	28 days after Visit 4b	28 days after last dose	
Time Window		1-5 days post ACS event	7-28days post ACS event	±2	±3	±2	±3	±4 days	
Blood and urine samples for safety laboratory evaluations (including fasting glucose) ^d		X ^{e,n}	x ^f	xª	x		x	x	
Efficacy Assessments:						2			
Spot urine for analysis of LTE ₄ levels and urinary creatinine		x ¹	x ^g	x (pre-dose)	x (pre-dose)		x(pre-dose)	x	Screening sample will not be used for assessment of primary endpoint
CFVR measurement			x		x	¢	x		· · · · · ·

Distribution:

Original:

Page 22 of 80

Copy:

TPCA025 Version 2 (based on TPQA036 Version 2) CONFIDENTIAL AND PROPRIETARY

Sponsor:	AstraZeneca AB	Protocol/CIP Number:	D7550C00003
CIL Project Number:	40343		

	ACS event	Visit 1 Screening	Visit 2 Randomization	Visit 3 (2 weeks) During Treatment	Visit 4 (4 weeks) During Treatment	Visit 4b (8 weeks) During Treatment	Visit 4c (12 weeks) End of Treatment	Visit 5 Follow-up	Comments
Study Day	-7 days	X ^a	day 1	day 14	day 28	28 days after Visit 4	28 days after Visit 4b	28 days after last dose	
Time Window		1-5 days post ACS event	7-28days post ACS event	±2	±3	±2	±3	±4 days	
Echocardiograp hy			X		x		x	X	
cfPWV/bPWA			x		x		x	x	
Pharmacokinet ics:							, ,		
Plasma for AZD5718			Xh	x ⁱ	x ^j		X ⁱ	x ^k	
Exploratory Clinical Variables:									
-PRO questionnaires			x (post-dose)		x (post-dose)		x (post-dose)		
-GRACE 2.0 Score		X							5
Exploratory Biomarkers:									

Distribution:

Original:

Page 23 of 80

Copy:

TPCA025 Version 2 (based on TPQA036 Version 2) CONFIDENTIAL AND PROPRIETARY

Sponsor:	AstraZeneca AB	Protocol/CIP Number:	D7550C00003
CIL Project Number:	40343		

	ACS event	Visit 1 Screening	Visit 2 Randomization	Visit 3 (2 weeks) During Treatment	Visit 4 (4 weeks) During Treatment	Visit 4b (8 weeks) During Treatment	Visit 4c (12 weeks) End of Treatment	Visit 5 Follow-up	Comments
Study Day	-7 days	X ^a	day 1	day 14	day 28	28 days after Visit 4	28 days after Visit 4b	28 days after last dose	
Time Window		1-5 days post ACS event	7-28days post ACS event	±2	±3	±2	±3	±4 days	
-Plasma for analysis of LTB4 levels		x ¹	x (pre-dose)	x (pre-dose)	x (pre-dose)		x (pre-dose)	x	
-Blood samples for cardiovascular biomarkers		x ¹	x (pre-dose)	x (pre-dose)	x (pre-dose)		x (pre-dose)	x	
-Plasma samples to be stored in biobank for exploratory analyses		x ¹	x (pre-dose)	x (pre-dose)	x (pre-dose)		x (pre-dose)	x	
-Optional Genetic sampling			X°						

a Screening during in-house stay after Acute Coronary Syndrome (ACS) event. Assessments can take place over several days. If the patient is discharged from hospital early, he/she may be asked to come back for blood sampling.

Original:

b Body weight assessments to be conducted in the mornings after an overnight fast, except for non-fasting at screening (Visit 1)

Distribution:

TPCA025 Version 2(based on TPQA036 Version 2)CONFIDENTIAL AND PROPRIETARYPage 24 of 80

Effective Date: 27th August 2017 Prior Effective Date: 21st December 2016

Copy:

Sponsor:	AstraZeneca AB	Protocol/CIP Number:	D7550C00003
CIL Project Number:	40343		

c Full physical examination at Screening (Visit 1) and at Follow-up (Visit 5), and brief physical examination on the other occasions (Visits 2, 3, 4 and 4c).

d Fasting plasma samples for glucose measurements to be obtained after an overnight fast (from 10 p.m. the evening before) at the same time point at Visits 2, 3, 4, 4c and 5 to the extent possible.

- e Will exclude fasting glucose measurement.
- f Liver panel analyses results will be used for assessment of exclusion criteria. Samples need to be analysed as acute samples.
- g Spot urine sample to be collected in the morning prior to screening and baseline assessments.
- h Baseline sample to be obtained in the morning before screening assessments. The other sample to be taken between 1-8 h post-dose.
- i C_{Trough} sample to be collected before dose administration at 20-28 hours after previous dose (dose on day 13 (day before Visit 3) and on day before Visit 4c).
- j Sampling times: pre-dose and then 0-2 h, 2-4 h, 4-8 h post dose. Sampling will be separated with at least 1 hour.
- k One PK-sample to be collected as suitable in relation to the other follow-up measurements. Exact sampling time to be entered in the CRF.
- 1 Sampling, where feasible, at 1, 2, 3 and 5 days post ACS. Exact sampling time to be entered in the CRF.
- m Unscheduled safety assessments (blood and urine samples for safety lab and ECG) may be performed as judged by the investigator.
- n Will exclude TSH, Free T3, Free T4 and Total T4.
- o The genetic sample may be collected at any time after randomization, however, ideally samples should be collected at Visit 2.

Order of assessments:

- 1. Spot urine sample for LTE₄ (u-LTE₄)
- 2. Safety labs, ECG, AE-review, physical examination and vital signs
- 3. Echocardiography, cfPWV/bPWA, (Vis 2, 4, 4c and 5) CFVR (Vis 2, 4 and 4c)
- 4. Sampling for Exploratory biomarkers and PK
- 5. Intake of IP
- 6. Meal
- 7. Post-dose PK sample no. 1 (Vis 2 and 4)
- 8. PRO (Vis 2, 4 and 4c)
- 9. Post-dose PK sample no. 2 (Vis 4)
- 10. Post-dose PK sample no. 3 (Vis 4)

Details on study procedures are reported in section 4.1 of the protocol.

Distribution:

Original:

Copy:

TPCA025 Version 2(based on TPQA036 Version 2)CONFIDENTIAL AND PROPRIETARYPage 25 of 80

Sponsor:	AstraZeneca AB	Protocol/CIP Number:	D7550C00003
CIL Project Number:	40343		

6.2 Time Point Algorithms

6.2.1 Relative Day

The date of first dose of IP will be considered relative Day 1, and the day before the first dose of study drug will be relative Day -1. Relative days will be calculated as follows only when the full assessment date is known (i.e., partial dates will have missing relative days):

- For days on or after the first dose of study drug: Date of Assessment Date of First Dose of IP + 1.
- For days before the first dose of study drug: Date of Assessment Date of First Dose of IP.

6.2.2 Windows

For the purpose of statistical analysis and if not otherwise specified, all the efficacy variables (primary, secondary and exploratory variables) and all the safety variables (Clinical laboratory evaluations, ECGs, Vital Signs and Physical examinations) will be assigned to the visit in which they are collected depending on the following analysis visit windows.

Analysis visit (AVISIT)	Scheduled visit day	Visit Window for Analysis (Days)
Baseline ^b	1	<]ª
Baseline Post-dose ^c	1	1
Visit 3	14	$10 - 18$ and $\leq = $ last dose
Visit 4	28	23 - 33 and <= last dose + 3
Visit 4b	56	49 – 63 and <= last dose
Visit 4c	84	74 – 94 and <= last dose + 3
Visit 5 – FUP 1 month	56 / 112	>=last dose + 24

Table 3: Visit windows

^a Includes also measurements collected at day 1 prior to first dose of IP for all variables except PRO questionnaires, ECGs, Vital Signs and Physical examinations. For PRO questionnaires, ECGs, Vital Signs and Physical examinations, all the measurements collected at day 1 will be considered as baseline measurements as per protocol. For uLTE₄ and cardiovascular biomarkers, the baseline will be the last available value before the first dose of treatment, among the values collected after the ACS event +7 days (included).

^b Analysis visit will be labelled "Baseline Pre-dose" for PK measurements.

^c Only applicable to PK measurements occurring on Day 1 after the first dose.

Measurements collected outside the visit windows will be labelled as "Unscheduled visit". For uLTE₄, urine creatinine, Creatinine-normalized u-LTE₄ and Cardiovascular biomarkers, measurements collected from date of ACS event to 6 days post ACS will be labelled as "Screening".

Distribution:

Original:

Copy:

TPCA025 Version 2 (based on TPQA036 Version 2)

STATISTICAL ANALYSIS PLAN

Sponsor:	AstraZeneca AB	Protocol/CIP Number:	D7550C00003
CIL Project Number:	40343		

In general, the baseline value used for statistical analyses is the last available value among those in the Baseline visit windows, prior to first dose of IP, except for PRO questionnaires. Additional details for baseline assessment will be given in section 6.3.

For visit windows 3, 4, 4b, 4c and 5 if more than one measurement of the variable (scheduled or unscheduled visit) falls in the same visit window but in different days, the nearest to the scheduled visit day will be taken. If several measurements are collected within the same distance from the scheduled study day, the data of the latest visit after the scheduled study day within that window will be used.

If several measurements are collected during the selected day, the average (for numeric values)/worst (for categorical values) of the measurements will be taken. For numeric values, the analysed value will be the arithmetic mean for normal distributed variables and the geometric mean for log-normal distributed variables.

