AZD5718, is a selective, reversible 5-lipoxygenase activating protein (FLAP) inhibitor which will attenuate production of pro-inflammatory and vasoactive leukotrienes by leukocytes e.g. neutrophils in the circulation encompassing both downstream cysteinyl leukotrienes measured as urine-leukotriene E4 (u-LTE₄) and leukotrienes measured as plasma LTB₄.

This Phase IIa Proof-of-Principle study will investigate if AZD5718, a FLAP inhibitor, can decrease u-LTE₄ levels and secondly if AZD5718 can improve CFVR as a measure of myocardial microvascular function. The study will also address safety and tolerability of AZD5718 on top of standard of care in CAD patients e.g. a post-ACS population. The result of the study will form the basis for the future clinical development programme for AZD5718 with the overall aim to investigate if AZD5718 can improve cardiovascular mortality and morbidity on top of standard of care in CAD patients.

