- Protocol section 8.3.1 stated that the efficacy analysis set will include all patients who were randomised, received at least one dose of study medication and have at least one baseline or postbaseline measurement. However, here it will have specified that this population will include all patients who were randomised, received at least one dose of study medication and have at least one baseline or postbaseline measurement for at least one of the efficacy variables (including all, primary secondary or exploratory variables).
- Protocol section 8.5.6 stated that an interim analysis plan will be prepared and finalized prior to the first administrative interim analysis. However, this interim analysis plan is based on a dedicated section of the SAP and there will be an update of the interim analysis charter before the second interim analysis.
- Protocol section 8.1 stated that any subsequent amendments to the SAP will be documented, with final amendments completed prior to unblinding of the data for the analysis. But it should be added that unblinded team will not be involved in any SAP amendment which will take place after the first unblinding for the first interim analysis.
- Protocol section 4.1 stated that CFVR measurement should be done before the IP intake during the visit. In the SAP, measurements done 3 days after last dose can be considered as the visit measurement.
- Protocol section 5.3.2 included a brief description of the question SF-36 V1 while V2 is used in the study. The wording was updated in the SAP to be consistent with the questionnaire SF-36 V2.

Distribution:

Original:

Copy:

TPCA025 Version 2 (based on TPQA036 Version 2) CONFIDENTIAL AND PROPRIETARY

Page 17 of 80

Sponsor:	AstraZeneca AB	Protocol/CIP Number:	D7550C00003
CIL Project Number:	40343		

- Protocol section 2.2 stated that standard model population PK parameters would be reported in a separate report. However, plasma concentrations will be part of the CSR and PK parameters described in a separate report.
- Protocol section 4.1 described an on-site Visit 5 (Follow-up). However, due to COVID19 situation, some phone visits replaced on-site visits. Protocol deviations were reported for each patient in that situation.

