6.4 Efficacy Variables

6.4.1 Primary Efficacy Variable(s)

Spot urine for analysis of LTE₄ levels (pmol/L) and urinary creatinine (mmol/L) will be collected at Visit 1, Visit 2, Visit 3 (pre-dose), Visit 4 (pre-dose), Visit 4c (pre-dose) and Visit 5. Primary efficacy variable is the Creatinine-normalized u-LTE₄ (pmol/mmol) which will be calculated as the u-LTE₄ / urinary creatinine. If the u-LTE₄ value falls under the limit of quantification (LoQ) then creatinine-normalized u-LTE₄ will be calculated as the limit/(sqrt(2)*creatinine). LoQ value will stated in the raw data.

The primary efficacy endpoint is the change at visit 4 (4 weeks) from Baseline in creatininenormalized u-LTE₄. The first secondary efficacy endpoint is the change at visit 4c (12 weeks) from Baseline in creatinine-normalized u-LTE₄.

Baseline Creatinine-normalized u-LTE4 value is defined as in section 6.3.

Creatinine-normalized u-LTE₄ is potential unblinding data. For the interim analysis these data will be provided only to the dedicated Covance unblinded team which will perform the analysis and send the results to the dedicated AZ unblinded team. Further details of the unblinding will be provided in the IA charter. For the final analysis these data will be provided to the Covance blinded team only after the database lock.

Distribution:

Original:

Copy:

TPCA025 Version 2 (based on TPQA036 Version 2)

Sponsor:	AstraZeneca AB	Protocol/CIP Number:	D7550C00003
CIL Project Number:	40343		

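### The three-day post-dose allowance at Visits 4 and 4c, introduced with reference to CFVR timing, also admits washout urine to the pre-dose u-LTE4 endpoints

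*SAP*

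**What the plan says.** SAP 6.2.2 assigns "all the efficacy variables (primary, secondary and exploratory variables) and all the safety variables" to visits through Table 3, unless otherwise specified. The Visit 4 window is "23 - 33 and <= last dose + 3" and the Visit 4c window is "74 – 94 and <= last dose + 3". The other on-treatment rows have no such allowance: Visit 4b is "49 – 63 and <= last dose", and Visit 3 carries the same cap at the last dose.

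SAP 5.2 lists the change from the protocol. That bullet opens with the protocol's requirement that CFVR be measured before the day's dose, and continues: "In the SAP, measurements done 3 days after last dose can be considered as the visit measurement". It names no other variable.

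Urine for u-LTE4 is planned before dosing at each on-treatment visit where it is collected (SAP 6.4.1: "Visit 3 (pre-dose), Visit 4 (pre-dose), Visit 4c (pre-dose"). SAP 8.6.1 puts Visits 3, 4 and 4c into one MMRM. I found no u-LTE4 rule on time since last dose in 6.2.2, 6.3, 6.4.1 or 8.6.1; the u-LTE4 rules in 6.2.2 and 6.3 concern screening and baseline. The Visit 3 and 4c trough PK sample is defined in SAP 6.1, footnote i: "sample to be collected before dose administration at 20-28 hours after previous dose".

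**The concern.** Protocol 1.1 says that AZD5718 "is a selective, reversible 5-lipoxygenase activating protein (FLAP) inhibitor", and dosing is once daily. A pre-dose sample is therefore a trough at about 24 hours, and the endpoint is inhibition at trough on treatment. A sample two or three days after the final dose measures a partly or fully washed-out state. Including it moves the active arms towards placebo, leaves placebo unchanged, and adds a second component to the active-arm spread. The rule governs the primary endpoint and the first secondary endpoint, yet the SAP's stated reason for it concerns an imaging measurement.

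The cut-off also changes between visits within one model. This is separate from the general question of how to treat patients who stop early, because each of these on-treatment rows already excludes samples by last-dose date. The question is whether that exclusion matches the definition of the endpoint.

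**Working it through.** **1. What each row accepts for u-LTE4.** Last dose means the final study dose (SAP 6.6.1 and 7.3). With morning dosing, day +1 is about 24 h, day +2 about 48 h and day +3 about 72 h.

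| Sample date relative to final dose | Visit 3 | Visits 4 and 4c |
|---|---|---|
| Same day, before the dose | kept | kept |
| Day +1 (about 24 h, the planned interval) | excluded | kept |
| Days +2 and +3 (about 48 to 72 h) | excluded | kept |
| Day +4 or later | excluded | excluded |

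A patient who takes a last dose on day 13 and gives urine on day 14 has an ordinary trough, but loses the Visit 3 value if treatment is never resumed. A patient who takes a last dose on day 25 and gives urine on day 28 has a three-day washout value counted at Visit 4.

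**2. Who can be affected.** At each clinic visit urine comes first and study drug fifth (order of assessments, SAP 6.1), and the Visit 4 and 4c doses are given at the site. A patient on schedule therefore has urine on or before the last-dose date. For the roughly 100 patients planned for 12 weeks, Visit 4 falls in mid-treatment and the cap does not bind unless they stop around then. For the roughly 38 patients on 4 weeks, Visit 4 is the end of treatment. If two samples fall in a window, the one nearest the scheduled day is used. What remains is mainly patients who stopped two or three days before Visit 4 or 4c and whose only sample in the window is late.

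**3. The plan's own figure.** SAP 4.5 gives 96% inhibition, SD below 4%, 33 per arm, an 80% threshold, one-sided 5%, and power above 99%. Taking SD 0.04 on a remaining fraction of 0.04:

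- log SD = sqrt(ln(1 + 1²)) = 0.833
- distance to threshold = ln 0.20 − ln 0.04 = 1.609
- SE = 0.833 × sqrt(2/33) = 0.205
- 1.609/0.205 − 1.645 = 6.2, so power exceeds 99.9%, and the stated figure reproduces.

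**4. Illustration of dilution in the high-dose arm.** The documents give neither the share f of washout samples nor the recovered level r relative to placebo, so both are assumed. The check uses one time point with a normal approximation, not the full MMRM.

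- mean log ratio = (1 − f) ln 0.04 + f ln r
- active-arm variance = 0.833² + f(1 − f)(ln r − ln 0.04)²
- SE = sqrt((active-arm variance + 0.833²)/33)

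| f | Inhibition, r = 1 | Power, r = 1 | Inhibition, r = 0.5 | Power, r = 0.5 |
|---|---|---|---|---|
| 0 | 96.0% | >99.9% | 96.0% | >99.9% |
| 5% | 95.3% | >99.9% | 95.5% | >99.9% |
| 10% | 94.5% | 99.9% | 94.9% | >99.9% |
| 20% | 92.4% | 93.8% | 93.4% | 99.3% |
| 30% | 89.5% | 62.4% | 91.5% | 90.6% |

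In patient counts, with 3 of 33 fully recovered (r = 1):

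- ratio = exp{(30/33) ln 0.04} = 0.054, against 0.040
- active-arm log SD = sqrt(0.693 + 0.0909 × 0.9091 × 3.219²) = 1.245, against 0.833
- SE = sqrt((1.549 + 0.693)/33) = 0.261
- one-sided 95% upper bound (t, 64 df) = 0.0536 × exp(1.669 × 0.261) = 0.083, against 0.056 with no washout and a threshold of 0.20.

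**The case against.** The strongest reply is that efficacy is ITT, the protocol wants all available data used, and patients off drug continue their visits. Keeping late samples is closer to that intention, and dilution works against the 80% claim. Visits 4 and 4c also end treatment for the two cohorts, which gives some reason for a longer limit there. The conservative direction stands, and so does the small number of samples. The ITT argument does not defend the rule as written, because Table 3 already removes samples from day +4 onward at Visits 4 and 4c and from day +1 onward at Visit 3. End of treatment justifies accepting a day +1 sample; it does not make days +2 and +3 pre-dose values.

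It can also be said that the operative sentence in SAP 5.2 speaks of measurements in general, so a wider allowance may have been meant. In that case 5.2 has not declared or justified it for the primary endpoint, and the sections still need reconciling.

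A reader might infer more than the documents support:

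- *That missing only the Visit 3 clinic dose loses that day's trough sample.* It does not. Last dose is the final study dose, so the sample is lost only after permanent stopping.
- *That the low-dose comparison could be pushed across the 80% inhibition threshold.* That comparison is outside the hierarchy and serves dose selection only. The dose to which the expected inhibition of around 90% in Protocol 1.2.1 refers is redacted, and a crossing depends on the chosen share and recovery.
- *That trough PK summaries are certainly contaminated.* The lead sentence of 6.2.2 does not list PK, the Table 3 footnotes on PK concern Day 1 labels, and SAP 8.6.3 summarises by protocol scheduled time. Section 7.1 summarises PK by visit, and I found no rule removing a late trough, so a clarification is warranted but no more.

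**Conclusion.** The inconsistency is real and lies in a stated rule. Table 3 extends to u-LTE4 an allowance that SAP 5.2 introduces for CFVR timing; days +2 and +3 conflict with the pre-dose definition; and Visit 3 uses a different limit in the same model. The bias is towards less inhibition and a larger SD. It does not threaten the high-dose test at any plausible share: power stays above 99% with 10% of active-arm values fully recovered, and material loss needs something like 20% to 30%, which the visit procedures make unlikely. These figures rest on the planning effect, a log SD of 0.833, 33 per arm, and assumed shares and recovery; the actual size cannot be obtained from the documents. The reason to act is that acceptance of samples for the primary endpoint should be explicit, consistent across visits and settled before unblinding.

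**What to change.** Reconcile SAP 5.2 and Table 3:

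- Limit the three-day allowance to CFVR and the other imaging and pulse-wave measurements, and name those variables in both places.
- For u-LTE4, use one limit at Visits 3, 4 and 4c: sample date no later than last dose + 1 day. This keeps every ordinary 24-hour sample, including the Visit 3 sample now lost after permanent stopping.
- Keep the excluded post-dose u-LTE4 values in a listing and in a sensitivity analysis on all available data, in line with the protocol's ITT wording.
- For the descriptive PK summary, report as Visit 3 and 4c trough only samples within the SAP's own 20-28 h definition, and list the rest with actual times.

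The cost is a change of wording and a few lines of derivation code. A few values leave the primary visit summary, but they remain visible in the listings, and the u-LTE4 values also in the sensitivity analysis.
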